1. SYNOPSIS

Study Title: A prospective, observational, non-comparative, open-label study to investigate the effectiveness of the treatment with weekly Alendronate in postmenopausal women with Osteoporosis.

Objectives:

The primary objective of this study is to evaluate Bone Mineral Density (BMD) changes at lumbar spine of Greek osteoporotic women from baseline to 12th month from the initiation of Alendronate 70mg once weekly.

The secondary objectives of this study are to estimate new vertebral and non-vertebral fragility fractures, hip fractures, treatment compliance, occurrence of back pain and days lost from work due to fracture related back pain from baseline to 12th month from the initiation of Alendronate 70mg once weekly. Also, to evaluate the safety of Alendronate assessed by the type, frequency, and severity of ADRs for 18 months after the initiation of study.

Design and Outcomes:

This is a Greek observational prospective study of 12 months to evaluate the effect of Alendronate 70mg once weekly on BMD change (%) at lumbar spine in postmenopausal women. The decision to treat the patient with Alendronate must be made independent of and prior to their enrollment in the study. Patients eligible to participate will receive their prescription monthly.

Primary Outcome:

- BMD change (%) at lumbar spine at 6,12 months of treatment measured by DXA

Secondary Outcomes:

- the proportion of patients with severe osteoporosis experiencing one or more new vertebral and non-vertebral fragility fractures assessed by spine radiographs regardless of symptoms
- Compliance to therapy, self-reported by patients
- Days lost from work due to fracture-related back pain, self reported by patients

Secondary Safety Outcomes:

- the proportion of patients with ADR to Alendronate
- the proportion of patients with serious ADR to Alendronate

Treatment Procedures and Duration:

Patients will return to the clinic every month to receive their Alendronate 70mg prescription. Patients will be observed for a period of up to 12 months after their entry in the study and will be followed up for 6 months after their last visit.

Sample Size and Population:

Inclusion criteria: Postmenopausal women who are diagnosed with osteoporosis.

Exclusion criteria: Previous treatment with drugs that modify bone metabolism or serious bone/esophageal/renal disease.

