4. STUDY OBJECTIVES

Primary objective:

Evaluate Bone Mineral Density (BMD) changes at lumbar spine of Greek osteoporotic women from baseline to 12th month from the initiation of Alendronate 70mg once weekly.

Secondary objectives:

Evaluate new vertebral and non-vertebral fragility fractures, hip fractures, treatment compliance, occurrence of back pain and days lost from work due to fracture related back pain from baseline to 12th month from the initiation of Alendronate 70mg once weekly.

Also evaluate the safety of Alendronate assessed by the type, frequency, and severity of ADRs for 18 months after the initiation of study.

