8. TREATMENT PROCEDURES AND STUDY PROCEDURES

This study is designed to follow and observe patients who will initiate treatment with Alendronate 70mg in routine clinical practice. No study-specific treatment will be provided and no additional clinical procedures or assessments will be required as part of this observational study. Patients will be observed for a period of up to 12 months after their entry in the study unless patients discontinue the study or are lost to follow up. Information regarding the clinical management of the patients receiving Alendronate 70mg may be collected whenever available, even after treatment discontinuation.

There are no procedures or changes to routine clinical management of patients. It is anticipated that patients will return to the clinic every month to receive their Alendronate 70mg prescription. Patients will be followed for approximately 6 months after their last visit. Available clinical information obtained for routine clinical practice (including those already recorded on the patient medical records ie, baseline characteristics) will be recorded, including Alendronate 70mg administration, previous and current therapies, medical history (including fracture history), ADRs and serious ADRs and co-morbidities.

Throughout the study, investigators may prescribe any concomitant medications or treatments deemed necessary to provide adequate routine clinical care including calcium and vitamin D supplementation, which will be recorded.

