10. STATISTICAL CONSIDERATIONS

Study Outcomes:

The following outcomes are to characterize/estimate the effectiveness during the first 12 months of treatment with Alendronate.

Primary outcome:

- BMD change (%) at lumbar spine at 6,12 months of treatment measured by DXA

Secondary outcomes:

- the proportion of patients with severe osteoporosis experiencing one or more new vertebral and non-vertebral fragility fractures assessed by spine radiographs regardless of symptoms
- Compliance to therapy, self-reported by patients
- Days lost from work due to fracture-related back pain, self reported by patients

The following secondary outcomes are to characterize the safety of patients during the first 12 months of treatment with Alendronate and during the 6 month follow up period:

- the proportion of patients with ADR to Alendronate
- the proportion of patients with serious ADR to Alendronate

The Full Analysis Set will consist of all enrolled patients satisfying the inclusion/exclusion criteria that receive at least 46 doses - 96% of the 48 that ideally would receive during the study duration- and have a non-missing enrollment date. All analyses will be performed on this analysis set.

Subsets and/or Covariates:

The following variables will be collected at baseline, either directly as part of routine clinical practice, or from medical records when available:

Demographic patient data:

- Educational level
- Patient employment status
- Patient living situation (at home with spouse/family, at home with care/support, at home alone, nursing home)

Medical condition regarding osteoporosis:

- Body mass index (≤ 25 or > 25 kg/m²)
- Age at menopause
- Cause of menopause (natural onset, clinically/surgically induced)
- Height loss since maximal height
- Height loss in centimeters (cm)
- Previous fracture
 - Previous hip fracture
 - Previous vertebral fracture
 - Other previous fractures
- Previous hospitalization for osteoporotic fracture and/or surgical osteoporotic fracture treatment
- One or more falls experienced during the past 12 months
- One or more episodes of immobility experienced during the past 12 months
- Parent fractured hip
- Current smoker
- Former smoker
- Systemic glucocorticoid use
- Secondary osteoporosis
- Alcohol consumption
- Femoral neck BMD T-score
- Lumbar spine BMD T-score
- Total hip BMD T-score

Patient-related:

- Age (years)
- Age group (< 65, ≥ 65 to <75, ≥ 75 years)
- Time since Post Menopausal Osteoporosis (PMO) diagnosis

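### The only fracture outcome relies on spine radiographs for vertebral and non-vertebral fractures alike, and hip fracture, a stated objective, has no outcome of its own

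*Protocol*

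**What the plan says.** Section 4 sets the secondary objectives: "Evaluate new vertebral and non-vertebral fragility fractures, hip fractures, treatment compliance, occurrence of back pain and days lost from work". Hip fractures are listed separately from vertebral and non-vertebral fractures, and nothing limits the fracture objectives to a subgroup.

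The outcome list in Section 10 contains one fracture outcome, worded identically in the Synopsis: the proportion of women with severe osteoporosis who have "one or more new vertebral and non-vertebral fragility fractures assessed by spine radiographs regardless of symptoms". No hip fracture outcome appears in either place. The only other effectiveness outcome that mentions fracture is "Days lost from work due to fracture-related back pain, self reported by patients", which is not a fracture count.

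On data sources, Section 8 states that "no additional clinical procedures or assessments will be required as part of this observational study". It has available routine information recorded, including "medical history (including fracture history), ADRs and serious ADRs and co-morbidities". The table in Section 14 marks medical history at enrolment only and has no row for fractures occurring on study. Section 10 adds only that bone fractures are summarised as counts and percentages, on observed values without imputation.

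**The concern.** A method of ascertainment determines what an outcome can contain. Here one method is attached to a pooled outcome, and it images only one of the two anatomical groups being pooled. The sentence therefore promises a proportion covering vertebral and non-vertebral fractures but names a tool that sees essentially the first. The objectives go further and single out the hip, for which no outcome exists.

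A reader of the final report would take the figure as the share of women with any new fragility fracture, and it would be too low for that. The observed-values rule could make this worse: a woman with a hip fracture and no spine film could be counted as missing rather than as a case. If non-vertebral fractures are not captured prospectively, a later analysis plan may be unable to recover them.

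**Working it through.** **Own figure.** The protocol gives no expected fracture risk and no precision for this outcome. Its one calculation, the sample size, concerns lumbar spine BMD and does not bear on this point.

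**Objectives against outcomes and methods.**

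| Objective (Section 4) | Outcome (Section 10, Synopsis) | Method named | Does the method image the site? |
|---|---|---|---|
| New vertebral fractures | Part of the pooled proportion | Spine radiographs | Yes |
| New non-vertebral fragility fractures | Part of the pooled proportion | Spine radiographs | Not the limb sites |
| Hip fractures | None of its own | None of its own | Not applicable |

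**Could another route supply the missing events?**

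- *Medical history, including fracture history (Section 8).* Recorded where available, but scheduled at enrolment only in Section 14 and not linked to the outcome.
- *Baseline fracture variables (Section 10).* Previous hip, vertebral and other fractures are separated at baseline. No on-study counterpart is listed.
- *Safety reporting (Section 11).* The investigator records an event as an ADR only if it is judged possibly related to alendronate. A hip fracture judged unrelated would not be recorded there.
- *Work days lost.* Limited to back pain, so limb fractures do not enter.

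None of these is named as a source for the fracture outcome.

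**Size, under assumed risks.** Let v and w be the 12-month risks of a vertebral and a non-vertebral fracture. Assume that they are independent, that films detect every vertebral fracture, and that films detect no non-vertebral one.

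- True proportion with any fracture = 1 − (1 − v)(1 − w)
- Proportion recorded by film = v
- Share of women with any fracture who are missed = 1 − v / [1 − (1 − v)(1 − w)]

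| v | w | Any fracture | Recorded | Share missed |
|---|---|---|---|---|
| 3% | 1% | 1 − 0.97 × 0.99 = 3.97% | 3% | 0.97/3.97 = 24% |
| 2% | 2% | 1 − 0.98 × 0.98 = 3.96% | 2% | 1.96/3.96 = 49% |
| 1% | 3% | 1 − 0.99 × 0.97 = 3.97% | 1% | 2.97/3.97 = 75% |

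The share missed does not depend on the number of women. Absolute numbers do, and they cannot be given. The outcome is restricted to severe osteoporosis, and Section 10 restricts every analysis to women with at least 46 of 48 doses. The protocol states the size of neither group.

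**The case against.** The strongest reply is that the phrase about spine radiographs regardless of symptoms is natural language for vertebral fractures, which may be silent, and was simply misplaced. That may be so, but the sentence does not say it, and the same wording stands in two places. If it was the intention, non-vertebral and hip fractures have no stated source, and the same amendment is needed.

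Second, a reader might infer that non-vertebral fractures will be zero by construction, or that hip fractures can never be estimated. The documents do not support that. Section 8 has available routine information recorded, the women are expected monthly at an orthopaedic clinic, and Section 10 does not confine its counts of bone fractures to film findings. A hip fracture requiring admission also meets a seriousness criterion in Section 11, and Section 12 has serious adverse events notified to the ethics committee. Some clinical fractures may therefore be on file. What stands is that none of these routes is tied to the outcome.

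Third, the missing fracture row in Section 14 is weak evidence by itself, since the table also has no row for DXA, compliance or work days lost. That is fair. The point rests on the outcome wording, and the table merely fails to repair it.

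Fourth, it is tempting to apply assumed risks to the 465 women of the sample-size calculation and quote numbers of lost cases. That denominator does not belong to this outcome, so such counts should not be used.

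**Conclusion.** The point holds. The one fracture outcome names a method that does not image most non-vertebral sites, and the hip objective has no outcome. Followed literally, the reported proportion would largely reflect vertebral fractures under a label that claims both kinds.

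On the assumed risks, about a quarter to three quarters of women with any fracture would be missed. That range follows directly from the assumed vertebral/non-vertebral split and from independence. It illustrates the size, and the defect itself rests on the text. Any fractures taken from routine records would reduce the loss by an unknown amount.

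The matter should be fixed but is not critical. It affects one descriptive secondary outcome in a single-arm study, and it leaves the BMD outcome, the sample size, the ADR outcomes and the vertebral part of this outcome untouched.

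**What to change.** Replace the pooled outcome, in the Synopsis and in Section 10, with three proportions:

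- (a) new vertebral fractures, by spine radiograph, with the wording on radiographs and symptoms confined to this part;
- (b) new non-vertebral fragility fractures, by patient report at the monthly visits, confirmed from the medical record or from routine-care imaging of the affected site;
- (c) hip fractures, ascertained as in (b).

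Add an on-study fracture row to the Section 14 table for the observation period and the end of study, recording site, date and whether the fracture was low-energy.

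Reconcile the restriction to severe osteoporosis with Section 4, whose fracture objectives carry no such limit. Either the outcomes cover all enrolled women or the objectives state the subgroup and how it is defined. Without this step the three proportions would still not match the objectives.

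The cost is amended wording and one added data item. Parts (b) and (c) need no new clinical procedure, because monthly attendance is already expected. Whether the films in part (a) can be obtained when no additional assessments are required is a separate question that this change does not settle.

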7. SELECTION AND ENROLLMENT OF SUBJECTS

Inclusion criteria:

- Postmenopausal women who are diagnosed with osteoporosis either by a DXA scan with a T score <-2.5 either by suffering a low intensity fracture (even in the absence of a DXA scan with T score <-2.5). The bone location that will be used in this study – lumbar spine- is among the recommended for evaluation of BMD by bone densitometry.
- Written informed consent

Exclusion criteria:

- Previous treatment with drugs that modify bone metabolism
- Renal failure (GFR <35 ml/min, as suggested by drug spc)
- History of reflux esophagitis, gastric or duodenal ulcers, gastrectomy

- Bone disease such as primary hyperparathyroidism, hyperthyroidism, Paget disease, Cushing syndrome, multiple myeloma, rheumatoid arthritis, or osteogenesis imperfecta.

Enrollment:

Patient pool will comprise of all patients attending the orthopaedic clinic of Larisa Public Hospital. The first 512 patients assessed in this clinic and recommended based on national guidelines and international good clinical practice that they need to be treated with biphosphonates, will be candidates to be enrolled in this study. All patients must sign the appropriate consent form before being enrolled into the study.

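### The only fracture outcome relies on spine films even for non-vertebral fractures and counts only women with severe osteoporosis, while the objective covers vertebral, non-vertebral and hip fractures with no severity limit

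*Protocol*

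**What the plan says.** **Objective.** Section 4 sets out to "Evaluate new vertebral and non-vertebral fragility fractures, hip fractures, treatment compliance, occurrence of back pain" and days off work. The Synopsis has the same scope: to "estimate new vertebral and non-vertebral fragility fractures, hip fractures, treatment compliance" and so on. Neither limits the objective by severity.

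**Outcome.** Section 10, repeated in the Synopsis, gives one fracture outcome. Its denominator and event are "the proportion of patients with severe osteoporosis experiencing one or more new vertebral and non-vertebral fragility fractures", and its means of assessment is contained in "new vertebral and non-vertebral fragility fractures assessed by spine radiographs regardless of symptoms".

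**Who is enrolled.** Section 7 admits "Postmenopausal women who are diagnosed with osteoporosis either by a DXA scan with a T score <-2.5 either by suffering a low intensity fracture". Severity is not an eligibility criterion.

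**What the study may ask for.** Section 8 says that "no additional clinical procedures or assessments will be required as part of this observational study". It adds that routine clinical information will be recorded and may be collected when available.

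**The concern.** An outcome should measure what its objective names, in the women the objective covers, by a method able to find the event. This outcome departs from the objective in two ways.

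- **Method.** A spine radiograph shows vertebrae. It does not show a hip, wrist or other non-vertebral fracture, yet it is the only method named for the whole outcome.
- **Population.** The objective takes in the enrolled women; the outcome counts only those with severe osteoporosis.

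The risk is one of interpretation. In a study of effectiveness with no comparator, a low count of non-vertebral or hip fractures could be read as a benefit of treatment when the plan had no systematic way of finding them. The reported proportion would also describe a subgroup and not the cohort named in the objective.

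**Working it through.** The protocol has no fracture figure to reproduce. Its only calculation, the sample size, concerns BMD: 1.96² × 0.051 × 0.949 / 0.02² = 464.8, rounded up to 465; 465 × 1.10 = 511.5, rounded up to 512. Both figures reproduce, but they set no target for fractures. The check is therefore a comparison of sections.

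**Step 1: objective against outcome.**

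| Item | Objective (Synopsis, Section 4) | Outcome (Synopsis, Section 10) |
|---|---|---|
| Population | No severity limit | Women with severe osteoporosis only |
| Vertebral fractures | Yes | Yes, by spine film |
| Non-vertebral fractures | Yes | Yes, but the only method named is spine film |
| Hip fractures | Named separately | Not separate; they fall under non-vertebral |
| Occurrence of back pain | Named | No outcome; only work days lost to fracture-related back pain |

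**Step 2: is there another route by which incident non-vertebral fractures would be recorded?**

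- Section 6 lists what is obtained at the monthly visits: alendronate prescription and administration, concomitant medication, and adverse drug reactions. Fractures are not listed.
- Section 8 mentions fracture history as part of medical history. The table in Section 14 ticks medical history at enrollment only.
- Section 11 has an event recorded as an adverse drug reaction when the investigator judges it possibly related to alendronate. A fragility fracture attributed to the disease would not enter by that route.
- Section 10, Data Analyses, promises counts and percentages for bone fractures but does not say how they are found.
- Section 8 permits collection of routine information when available. That allows incidental capture and sets no schedule for it.

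**Step 3: does the reading of the sentence matter?** If spine films apply to both fracture types, the method cannot show the non-vertebral ones. If they were meant for vertebral fractures only, the non-vertebral ones have no stated method. Ascertainment is deficient either way, and the severity restriction is unaffected.

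**Step 4: the imaging wording.** Counting fractures whether or not they cause symptoms suggests films taken irrespective of symptoms. Section 8 requires no assessments beyond routine care. The two can coexist only if routine care already supplies such films, which the protocol does not say.

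**The case against.** **Loose drafting.** The spine-film phrase may have been meant for vertebral fractures alone. That is plausible, but it leaves non-vertebral fractures without any method.

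**Routine care will catch them.** Patients are expected monthly at an orthopaedic clinic, and Section 8 lets routine information be recorded. This stands in part. A reader might infer that non-vertebral and hip fractures would be missed altogether; the documents do not support that, because some would be captured incidentally. Under-ascertainment is the supportable claim. Nor is there any basis for saying what fraction of the combined outcome is lost.

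**The Section 14 table is not exhaustive.** Correct. It also has no row for DXA, although BMD is the primary outcome. The absence of a fracture or radiograph row therefore proves little by itself. The point rests on the outcome wording together with Sections 6, 8 and 11.

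**Hip fractures and back pain are covered.** Hip fractures are non-vertebral, so they lie within the outcome; what is missing is a separate report of them. Days off work for fracture-related back pain is a listed outcome. Only the occurrence of back pain has none.

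**New fractures could not be told from old.** A reader might infer this because no baseline film is specified. It is too absolute: Section 10 collects previous hip, vertebral and other fractures at baseline. Silent vertebral fractures present at entry remain a difficulty.

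**A definition of severe osteoporosis can sit in the SAP.** Agreed, and its absence here is not the point. Using the severe group as the denominator is fixed in the protocol and conflicts with the objective whatever definition is chosen.

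**Conclusion.** The concern holds for a secondary, descriptive outcome; the primary BMD outcome is not affected. The protocol fixes a fracture outcome that differs from its own objective on population and on the means of finding non-vertebral fractures, and no other section supplies a scheduled alternative. Two consequences follow: non-vertebral and hip fractures are likely to be under-ascertained, and every woman not classed as severe is left out of an objective that covers her.

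The direction is clear, but the size cannot be stated. The share of women with severe osteoporosis and the fracture incidence over 12 months are not in the document, and no precision is promised for fractures. A reader might infer that most of the cohort is discarded, or that the confidence interval becomes unacceptably wide. Either would require assumed values and a target that the protocol does not set.

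The conclusion assumes only that spine films do not image non-vertebral sites and that incidental capture from routine care is incomplete.

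**What to change.** Replace the fracture outcome in the Synopsis and Section 10 with two outcomes.

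- **(a) Non-vertebral.** The proportion of all women in the analysis population with a new clinical non-vertebral fracture, with hip reported separately. Record it from patient report at the monthly visits already anticipated, and confirm it from the medical record or an existing radiology report.
- **(b) Vertebral.** New clinical vertebral fractures for all women in the analysis population. Report new radiographic fractures only for women with both a baseline and a follow-up spine film from routine care. State how many women have paired films and that this group may be selected.

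Then:

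- report severe osteoporosis as a subgroup and not as the denominator;
- reconcile the wording on symptoms in Section 10 with the statement in Section 8 that no further assessments are required;
- add occurrence of back pain as an outcome, or remove it from the objectives.

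**Cost.** One added eCRF field and reliance on self-report with confirmation from records. Section 10 already accepts self-report for compliance and days off work. No imaging is added. For that reason the paired-film group in (b) may remain selected; the change makes its denominator explicit but does not remove the selection. If asking about fractures at each visit is regarded as an added assessment, Section 8 should say that this recording is permitted.

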9. REMOVAL AND REPLACEMENT OF PATIENTS

Removal of Patients:

Patients have the right to withdraw fully from the study at any time and for any reason without prejudice to her future medical care by the physician or at the institution. Withdrawal of full consent for this study means that the patient does not wish to or is unable to continue further study participation; patient data up to withdrawal of consent will be included in the analysis of the study. The investigator will discuss with the patient appropriate procedures for withdrawal from the study. Should a patient (or a legally acceptable representative) request or decide to withdraw from the study, all efforts will be made to complete and report the observations as thoroughly as possible up to the date of withdrawal. All information should be reported on the applicable eCRFs.

Replacement of Patients:

Participants who withdraw from the study or lost to follow-up will not be replaced.

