- Number of comorbidities
- Any chronic medical condition
- Type of chronic medical condition (diabetes/osteoporosis/hypertension/other)

Sample Size:

A review of published data highlighted that BMD change at lumbar spine at 12 months for postmenopausal women on alendronate 70mg weekly ranges from 3.7%-5.1%.¹³⁻¹⁵

Taking into account the most unfavourable result, which is 5.1%, we will estimate the sample size of our study. We will conduct an observational study which intends to investigate the Lumbar Spine BMD (%) change from baseline to 12 months (single proportion).

Published data estimate that Lumbar Spine BMD increases 5.1% from baseline to 12 months.

We would like to ensure that 95% CI of the Lumbar Spine BMD change (%) is estimated with precision ±2% (i.e. with a margin of error of 2%).

The required sample size would be $n \geq \frac{z^2}{\delta^2} p(1-p) \rightarrow n \geq \frac{1.96^2}{0.02^2} 0.051(1-0.051) \rightarrow n \geq 465$

If we add 10% to compensate for potential loss of subjects, the final number will sum up to $n \geq 512$ patients.

Thus in order to have sufficient precision and compensate for potential loss of subjects the final sample size should be 512 patients.

Data Analyses

This is an observational study for which the analysis will be descriptive in nature and no formal hypothesis will be tested. T test will be used to assess the change in BMD between baseline and end of study measurements. Significance was indicated at $P < 0.05$.

For quantitative parameters (BMD, days lost from work) mean, standard deviation, median, range (minimum and maximum), as well as number of missing data (if relevant) will be displayed. For qualitative parameters (bone fractures) counts, percentages and number of missing data if relevant will be displayed. Treatment compliance for each patient will be calculated as the number of doses study drug was actually taken, with the maximum count being 48. Compliance will be regarded as a quantitative parameter.

In general, missing values will remain as missing, i.e., no attempt will be made to impute missing values and only observed values will be used in data analyses and presentations.

Baseline characteristics will be described. Demographics, medical history and other baseline variables will be summarized as appropriate to the type of data.

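### The only analysis set keeps women with at least 46 of 48 doses, so every result, including compliance and safety, is conditioned on adherence after enrolment and conflicts with the rule on withdrawals

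*Protocol*

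**What the plan says.** Protocol Section 10 (Study Outcomes) restricts the Full Analysis Set to enrolled women who meet the eligibility criteria, have an enrolment date, and "receive at least 46 doses - 96% of the 48 that ideally would receive during the study duration". It continues: "All analyses will be performed on this analysis set". The protocol names no all-treated, safety or sensitivity set.

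The aim is given in the same section: "The following outcomes are to characterize/estimate the effectiveness during the first 12 months of treatment with Alendronate". Section 8 gives the setting: "This study is designed to follow and observe patients who will initiate treatment with Alendronate 70mg in routine clinical practice".

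Other provisions that bear on the set:

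- Section 9, on women who withdraw: "patient data up to withdrawal of consent will be included in the analysis of the study". Women who withdraw or are lost are not replaced.
- Section 8, on information about clinical management: it "may be collected whenever available, even after treatment discontinuation".
- Section 10 (Data Analyses): missing values are not imputed and "only observed values will be used in data analyses and presentations". Compliance is the number of doses taken, with a maximum of 48.
- Section 10 (Sample Size): "If we add 10% to compensate for potential loss of subjects, the final number will sum up to" 512, starting from 465.
- Section 11: all ADRs from the first administration to the end of the 6-month follow-up are to be captured.

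**The concern.** Whether a woman belongs to the set is known only near the end of treatment. Anyone who misses three or more doses, or who stops, withdraws, is lost or dies before dose 46, drops out of every result. The set has the name of an inclusive population but the content of a strict per-protocol one.

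Three things are at stake. First, the results would describe near-complete adherers, while the study sets out to describe women who start the drug in ordinary care. Second, two outcomes are altered by construction: compliance is measured only among women selected for being compliant, and ADR proportions are measured only among women who stayed on the drug almost throughout. Third, Sections 9 and 10 cannot both be followed for a woman who withdraws consent before dose 46.

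**Working it through.** **1. The threshold.** 46/48 = 0.958, which rounds to the stated 96%. With 45 doses, 45/48 = 0.938, and the woman is excluded. At most two doses may be missed. Forty-eight doses over 12 monthly prescriptions is 4 per month, so if doses follow the prescriptions, one missed month leaves 48 − 4 = 44 and excludes her.

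**2. Section 9 against Section 10.** Section 9 says that data up to withdrawal of consent enter the analysis. Section 10 says that every analysis uses the set with at least 46 doses. A woman who withdraws consent before dose 46 is in the analysis under one rule and outside it under the other.

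**3. Compliance.** The outcome counts doses taken, up to 48. Inside the set it can take only three values (46, 47, 48), that is 95.8% to 100%, whatever happened in the cohort.

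**4. ADRs.** Section 11 has all reactions captured from the first dose, but Section 10 then drops those in women who stopped or died before dose 46. Let p be the true ADR proportion, s the share of women with an ADR who are excluded, and o the share of other women who are excluded. The set shows p(1−s) / [p(1−s) + (1−p)(1−o)]. The documents give none of these, so the values below are assumptions:

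- p = 10%, s = 50%, o = 10%: 0.050 / (0.050 + 0.810) = 5.8%.
- p = 10%, s = 50%, o = 30%: 0.050 / (0.050 + 0.630) = 7.4%.
- p = 10%, s = 25%, o = 30%: 0.075 / (0.075 + 0.630) = 10.6%.

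The proportion is understated when women with an ADR are excluded more often than the others (s > o), which is the likely case if reactions cause stopping. In the third line s < o, and it is slightly overstated.

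**5. BMD gain.** Let a be the mean gain in the set, q the share of women who reach 46 doses, and f the gain in excluded women as a fraction of a. The all-patient mean is qa + (1−q)fa, so the overstatement is (1−q)(1−f)a. The value a = 5.1% is the figure used in the sample size section and stands in here for the mean in the set; q and f are assumptions.

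| q | All-patient mean, f = 0 | Overstatement, f = 0 | All-patient mean, f = 0.8 | Overstatement, f = 0.8 |
|---|---|---|---|---|
| 0.9 | 4.59% | 0.51 points | 5.00% | 0.10 points |
| 0.7 | 3.57% | 1.53 points | 4.79% | 0.31 points |
| 0.5 | 2.55% | 2.55 points | 4.59% | 0.51 points |

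The range is 0.1 to 2.6 points. With a = 3.7%, the lower end of the published range that the protocol cites, it is 0.07 to 1.85 points. At f = 1 it is zero.

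**6. The 10% allowance.** The plan's figures reproduce: 1.96² / 0.02² × 0.051 × 0.949 = 464.8, so 465; and 465 × 1.10 = 511.5, so 512. Keeping 465 leaves room for 512 − 465 = 47 exclusions, or 47/512 = 9.2%, for loss, non-adherence and missing BMD together. By the protocol's own formula, the half-width would be ±2.28% with 358 women (if 70% qualify) and ±2.69% with 256 (if 50% qualify).

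**The case against.** Section 5 also says that the study will confirm efficacy in the Greek population, and an adherent set serves that purpose. This stands as a reason to keep such a set, but not to make it the only one or to call it the Full Analysis Set.

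A statistical analysis plan may exist and often settles populations. That does not help here, because the protocol itself fixes the set and applies it to all analyses.

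Several stronger readings are tempting, but the documents do not support them:

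- A reader might infer that Section 8 also contradicts the set. It only permits collection of information after discontinuation and says nothing about analysis. The one contradiction is with Section 9, and it concerns withdrawal of consent before dose 46, not missed doses or stopping the drug.
- A reader might treat the overstated BMD gain as established, or attach one figure to it. The direction is plausible because excluded women have had less drug, but no document gives the share who qualify or the gain in the others. The same holds for fractures: a woman who fractures and still reaches 46 doses stays in the set.
- A reader might infer that the smaller set must miss the ±2% precision target. That follows from the protocol's single-proportion formula. If the percent change is treated as a mean with an assumed SD of 5, even 205 women (40% of 512) give 1.96 × 5 / √205 = ±0.68, well inside the target.
- A reader might say that more than 10% are expected to miss three doses. The protocol states no expected adherence; it only leaves little room for it.

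**Conclusion.** The point holds and should be corrected before analysis, since one definition governs the primary, secondary and safety results. Four parts need no assumed figure: the set selects on adherence after enrolment, it conflicts with Section 9 for women who withdraw before dose 46, it confines compliance to 46-48 doses, and it removes from the ADR and serious ADR proportions the women who stop or die before dose 46.

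Overstatement of the BMD gain is an expected direction, not a demonstrated amount. The range of 0.1 to 2.6 points rests on assumed q of 50-90%, f of 0-80% and a 5.1% gain in the set. The margin of 47 exclusions follows from the protocol's own numbers; whether it would be exceeded cannot be told from the documents.

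**What to change.** - Define the Full Analysis Set as all eligible enrolled women with at least one dose, regardless of later adherence. For the BMD outcome, also require a baseline lumbar spine DXA.
- Analyse ADRs, serious ADRs and compliance in all treated women.
- Keep the group with at least 46 doses as a per-protocol sensitivity set, labelled as such.
- Reconcile Sections 9 and 10, so that the rule on data up to withdrawal and the definition of the set agree.
- Include scans that are available after discontinuation. A repeated-measures model using the 6- and 12-month scans is optional. It lets women with only one post-baseline scan contribute, but it cannot by itself remove the bias if women who stop have no scans.

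The cost is a changed definition and some extra tables, with no added visits or procedures. The headline BMD gain will probably be smaller. Because Section 8 requires no additional assessments, women who stop early may have few scans, so the number with BMD at each time point should be reported beside the result.
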